### Risks/Discomforts/Inconveniences

Risks that could be encountered during the study period

Risks associated with assessments:

Patients are assessed in person by experienced clinicians for discomfort or frustration associated with psychiatric interviewing or filling out questionnaires. Study clinicians are skilled at dealing with these events and will make efforts to help clients to feel as comfortable as possible (e.g., by giving breaks during an evaluation, offering encouragement).

Risks associated with EX/RP:

In EX/RP (an evidence-based treatment for OCD), patients confront feared situations that are expected to produce moderate levels of distress initially. This initial fear reaction is essential to the treatment, as it allows the patient to habituate to situations in which he or she is excessively or irrationally fearful.

Risks associated with nabilone: (see package insert):

Chemically, nabilone is similar to the active ingredient found in naturally occurring Cannabis (marijuana) or THC. It is thought to interact with the cannabinoid receptor system in the brain.

According to the package insert approved by the FDA, the most common adverse reactions to nabilone in controlled clinical trials were drowsiness, vertigo, dry mouth, euphoria (feeling "high"), ataxia, headache, and concentration difficulties. Caution is recommended when administering nabilone in combination with any CNS depressant. The effects of nabilone have not been studied in pregnant or nursing women.

Accurate estimates of the estimates of the incidence of adverse events associated with any drug are difficult to obtain because these estimates are influenced by factors such as drug dose and detection technique. The table presented below indicates the relative frequency of adverse events in placebo controlled clinical trials.

#### Incidence of Adverse Reactions in Placebo-Controlled Studies

Adverse Event	Nabilone (n=132) Percent	Placebo (n=119) Percent
Vertigo	52%	3%
Drowsiness	52%	5%
Dry Mouth	36%	2%
Ataxia	14%	0%
Euphoria	11%	1%
Sleep Disturbance	11%	1%
Dysphoria	9%	0%
Headache	6%	0%

---

Nausea	4%	0%
Disorientation	2%	0%
Depersonalization	2%	1%

Nabilone is a Schedule II controlled substance. However, the abuse potential of nabilone has been found to be low compared to other cannabinoids (Ware and Arnaud-Trempe, 2010).

Describe procedures for minimizing risks

1. Subjects with medical and psychiatric co-morbidity (e.g., psychosis) that make participation unsafe will not be eligible.
2. Subjects with a history of substance use disorder in the last year or an adverse experience with a cannabinoid will be excluded.
3. Subjects who enroll in the study will be assessed and monitored weekly by study physicians and an independent evaluator. Worsening of clinical symptoms or adverse side effects from nabilone can lead to study discontinuation.
4. A low dose of nabilone will be used (1 mg BID).

## Methods to Protect Confidentiality

Describe methods to protect confidentiality

All records will be kept confidential to the extent permitted by law. Paper records will be stored in locked files; electronic data will be saved on computers protected by passwords, secure logon, and data communications security procedures. The patient's name and other personal identifying information will be stored in an electronically secure database at New York State Psychiatric Institute. Records will only be available to research staff, and Federal, State, and Institutional regulatory personnel who may review the records as part of routine audits. A description of this clinical trial will be available on <http://www.ClinicalTrials.gov>, as required by U.S. Law. This Web site will not include information that can identify subjects. At most, the Web site will include a summary of the results. Patients can search this Web site at any time.

In regards to RecruitMe: All participant data will be protected under CUMC security policy. Only site administrators (also known as super users) will have full access to participant data. The data is limited to

basic contact information (i.e. name, phone, address) as well as their date of birth. Users that express interest in a specific study will have their contact information given to the study research team by a SA. SAs will be the only persons with access to the contact information. An automatic notification message will go out to investigators indicating that a person has expressed interest in their study. The message will also indicate that they will receive the contact information from the SA within a few days. Prospective participants will be required to accept the Terms of Service (TOS) within the Registry Form. By accepting the TOS, users will give their consent to have their contact information be stored on CUMC's secure database as well as allow investigators access to their information.

*Will the study be conducted under a certificate of confidentiality?*

No

## Direct Benefits to Subjects

Direct Benefits to Subjects

All of the patients in our study will be offered the gold standard psychotherapy for OCD (EX/RP), either in combination with the novel medication or in isolation in open treatment in our clinic after the four week medication trial. In addition, the findings of this study will increase knowledge of how to improve OCD treatment.

## Compensation and/or Reimbursement

Will compensation or reimbursement for expenses be offered to subjects?

Yes

Please describe and indicate total amount and schedule of payment(s).

Include justification for compensation amounts and indicate if there are bonus payments.

Participants will be compensated \$100 for completing the independent assessment and the cognitive testing (paid in cash during your visit at Week4). Additionally, participants can earn between \$24 and \$60 in two of the cognitive tasks (paid in cash at the end of the cognitive testing session at Week0).

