## Description of Subject Population

### Sample #1

Specify subject population

Adult individuals with OCD

Number of completers required to accomplish study aims

20

Projected number of subjects who will be enrolled to obtain required number of completers

25

Age range of subject population

18-60

Gender, Racial and Ethnic Breakdown

Based on the community from which we will be drawing subjects and proportions to those encountered

during previous clinical trials at this site, we expect the sample to be approximately 5% Hispanic and 95% Non-Hispanic; racially there will be 89% White, 9% Black, 2% Asian. Based upon the prevalence of OCD, it is expected that the sample will be approximately 1:1 =male:female.

Description of subject population

Female and male adults with a diagnosis of OCD and clinically significant symptoms (i.e., a Y-BOCS score of at least 16). Minorities and females will be well represented in this study.

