## Study Procedures

Describe the procedures required for this study

Screening/initial evaluation

Patients deemed eligible following screening (by phone or in person) will undergo with their consent: 1) an evaluation by a senior clinician (M.D. or Ph.D.); 2) a Structured Clinical Interview for DSM-5; 3) a Y-BOCS to assess OCD severity; and 4) a medical evaluation (i.e., history, physical, routine blood tests [including blood pregnancy test for females], urine toxicology, and EKG). Those who meet entry criteria will provide written informed consent.

Randomization and Treatment Intervention

After the baseline evaluation, participants will be randomized to one of two groups. Randomized assignments (stratified by SSRI use) will be generated using a random number generator in SPSS.

Group 1 (n=10) will receive nabilone at 1 mg BID over 4 weeks. (Note: These patients will be offered EX/RP at no cost in open treatment after the 4 weeks of the trial).

Group 2 (n=10) will receive nabilone at 1 mg BID plus therapist-guided EX/RP (as described below) during 4 weeks.

All subjects will meet weekly with a study psychiatrist to receive nabilone and to review side effects.

Those randomized to EX/RP will also meet with a study therapist (MA or PhD-level) to receive 9 sessions of EX/RP (i.e., a treatment planning session plus 8 sessions of EX/RP) over four weeks according to a treatment manual. Following standard procedures, EX/RP will include therapist-aided exposure, self-guided exposure as homework, ritual prevention, and education about relapse prevention.

Assessments (independent evaluator)

An independent evaluator (Master's level or above) who is not involved with study treatment will assess global psychopathology (CGI); OCD symptoms (YBOCS); sensory phenomenon (Sao Paulo Sensory Phenomena Scale), depressive symptoms (HAM-D) **and at follow-up, any changes in treatment since study end and adherence to EX/RP lifestyle**. Subjects will also complete self-reports that assess depression and anxiety (DASS) and quality of life (Q-LES-Q). Subjects will be evaluated at weeks 0, 1, 2, 3, and 4 and also 1 month after study end (week 8, by phone or in person).

You can upload charts or diagrams if any

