## Criteria for Early Discontinuation

### Criteria for Early Discontinuation

Participants are free to withdraw from the study at any time for any reason. Study doctors are to discontinue patients from the study if patients:

- Request early discontinuation or withdraw consent.
- Experience a serious or intolerable adverse event that prevents the patient from continuing.
- In the Investigator's opinion, are experiencing a clinically significant deterioration in OCD (i.e., YBOCS score six points greater than their baseline at any time point).
- In the Investigator's opinion, are experiencing a clinically significant deterioration in a comorbid condition such as major depression. For example, if a patient became suicidal or their symptoms of depression increased such that the depressive symptoms were much or very much worse relative to baseline and the HDRS-17 is no longer <25, they would be discontinued from the study.
- Commit a protocol violation, including lack of compliance.
- Are "lost to follow-up."
- Encounter other conditions (such as administrative issues or pregnancy).

If a patient discontinues from the study at any time at their own request or at the study doctor's discretion, the reason(s) for discontinuation are to be recorded by the study. Subjects will be asked to return to the study site for final safety assessments as scheduled for the final study visit. Patients withdrawing from the study for reasons related to the study medication (usually adverse events) will be followed until the event(s) have resolved or no further action is required.

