- History of any significant medical condition that may increase the risk of participation

Interventions

Intervention Name (use generic name if established): Nabilone

Intervention Type: Drug

Intervention Description (do not repeat information already included in arm/group descriptions): Nabilone is a synthetic form of THC and cannabinoid 1 receptor agonist. It acts on the brain's "endocannabinoid system," which has been hypothesized to play a role in OCD.

Intervention Name: Exposure and Response Prevention Therapy

Intervention Type: Behavioral

Intervention Description: Exposure and Response Prevention Therapy (EX/RP) is a type of Cognitive-Behavioral Therapy for OCD that involves intentionally confronting situations that trigger obsessional distress while refraining from doing compulsions.

Outcome Measures

Primary Outcome Measure 1: Feasibility of recruitment of patients with OCD into a study of nabilone

Time Frame: Total participants who consent to participate for the duration of the study

Safety Issue (Is this outcome measure assessing a safety issue?): No

Primary Outcome Measure 2: Tolerability of nabilone (e.g. adverse events reported)

Time Frame: Baseline (Week 0), Week 1, Week 2, Week 3, Week 4

Safety Issue (Is this outcome measure assessing a safety issue?): Yes

Primary Outcome Measure 3: Yale-Brown Obsessive-Compulsive Scale (YBOCS)

Time Frame: Weeks 0 and 4

Safety Issue (Is this outcome measure assessing a safety issue?): No

Secondary Outcome Measures: Hamilton Depression Rating Scale, 17-Item (HDRS-17)

Time Frame: Weeks 0 and 4

Safety Issue?: No

Statistical Analysis Plan

For both the YBOCS and HDRS-17 measures, we will calculate change scores for the nabilone and nabilone+EX/RP groups based on the difference between Baseline (Week 0) and Week 4. This preliminary study is not designed to assess for statistical differences between groups, and thus only the overall magnitude of change between groups will be compared. We will assess feasibility of recruitment based on the total number of participants enrolled over the duration of the study. Finally, we will assess nabilone's tolerability in OCD based on weekly self-reporting of side effects using a checklist drawn from the nabilone package insert, and any other adverse events that occur over the course of the study.

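### Patients discontinued from the study are asked back for safety assessments, with no stated Week 4 Y-BOCS or HDRS-17 rating and no stated payment, so change scores may be missing mainly in those who did badly

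*Protocol*

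**What the plan says.** Four parts of the documents bear on this point.

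- **Payment** (Protocol, Compensation and/or Reimbursement). A sum of $100 is paid "for completing the independent assessment and the cognitive testing (paid in cash during your visit at Week4"). A further $24 to $60 can be earned "in two of the cognitive tasks (paid in cash at the end of the cognitive testing session at Week0"). No other payment is listed. Nothing is said about part payment or about patients who stop early.
- **Early discontinuation** (Protocol, Criteria for Early Discontinuation). Study doctors take patients out of the study if, among other reasons, they "Experience a serious or intolerable adverse event that prevents the patient from continuing", or if their OCD worsens, with a Y-BOCS six points above baseline as the marker. Afterwards, "Subjects will be asked to return to the study site for final safety assessments as scheduled for the final study visit". The section mentions no independent evaluator, Y-BOCS, HDRS-17 or payment at that return.
- **Assessment schedule** (Protocol, Study Procedures). "Subjects will be evaluated at weeks 0, 1, 2, 3, and 4 and also 1 month after study end". The independent evaluator rates the Y-BOCS and the depression scale.
- **Analysis** (SAP, Outcome Measures and Statistical Analysis Plan). Y-BOCS is a primary outcome and HDRS-17 the secondary one. Both are analysed as change scores "based on the difference between Baseline (Week 0) and Week 4". The SAP has no rule for a missing Week 4 score.

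**The concern.** The reasons for removal include poor tolerability and worsening OCD. If removal also ends efficacy rating, the missing Week 4 scores are related to the outcome: they are absent because the patient was doing badly. The mean change among patients with a Week 4 score would then tend to overstate improvement among all who started.

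This matters more than usual here because the descriptive change is the whole efficacy result. The SAP plans no between-group test and no handling of missing data, and the protocol intends the data to support grant applications. Side effects are also expected: the protocol's own table gives vertigo and drowsiness at 52% each on nabilone. If losses differ between the two arms, the planned comparison of the magnitude of change is affected as well.

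The payment text adds to the uncertainty. Most of the compensation is tied to the Week 4 assessment, but a discontinued patient cannot tell from the protocol whether that assessment, or its payment, is still open to them.

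**Working it through.** The documents give no figure for this point (no dropout rate, standard deviation or expected change), so there is nothing to reproduce. The check is a reading of the text plus simple arithmetic.

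**1. What a discontinued patient provides, as written.** The schedule calls for independent ratings at Weeks 0 to 4. The discontinuation section removes the patient from the study, not just from nabilone, and then names safety assessments at the return. The reference to the final study visit can be read in two ways:
- It fixes only the timing of the return. No Week 4 Y-BOCS or HDRS-17 is then obtained.
- It brings in everything done at that visit. Both scores are then obtained, and the payment condition could be met.

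The text does not settle which is meant. The SAP needs the Week 4 scores under either reading. Ratings at Weeks 1 to 3 may exist for such a patient, but the SAP does not use them.

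**2. How much of the compensation is at issue.** Share at Week 4 = 100 / (100 + Week 0 earnings).
- Week 0 earnings of $24: 100 / 124 = 80.6%, so 19.4% is already paid.
- Week 0 earnings of $60: 100 / 160 = 62.5%, so 37.5% is already paid.

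**3. How many patients might be affected.** Under Sample #1, "Number of completers required to accomplish study aims" is answered with 20, and "Projected number of subjects who will be enrolled to obtain required number of completers" with 25. The difference is 25 − 20 = 5, or 5 / 25 = 20%. This is a projection, and neither a dropout rate nor reasons are stated.

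**4. Illustrative size.** Let *m* be the mean improvement in the 20 patients with scores, and let the 5 without scores have improved by *d* points less (assumption). The mean over all 25 is

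(20*m* + 5(*m* − *d*)) / 25 = *m* − 0.20*d*,

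so the 20 with scores overstate the mean improvement by 0.20*d*:
- *d* = 3: 0.6 points
- *d* = 6: 1.2 points
- *d* = 9: 1.8 points

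More generally, if *k* of 25 lack scores, the overstatement is *k* × *d* / 25. With *k* = 2 and *d* = 6 it is 12 / 25 = 0.48 points.

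**5. Cognitive testing as a payment condition.** It appears in the compensation section but not in Study Procedures, Assessment Instruments or the SAP. The only session with a date is at Week 0.

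**6. Cost ceiling.** Paying all five projected non-completers: 5 × $100 = $500. Assessment Instruments gives 45 minutes for the Y-BOCS and 5 for the HDRS-17, so 50 minutes of rating per returning patient.

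**The case against.** **Forfeiture and incentives.** A reader might infer that patients who stop lose the $100, that the payment rewards staying on nabilone, or that it removes the incentive to give a Week 4 rating. The documents support none of these. The payment is for assessments, not for taking the drug, and forfeiture would be an inference from silence. A patient off nabilone who returns and is rated could qualify. The $100 is itself an incentive to attend Week 4. This objection stands in full.

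**Effect on the other primary outcomes.** Feasibility is judged by the number enrolled, and tolerability by weekly checklists plus any other adverse events. Side effects before dropout are therefore recorded, and withdrawals related to the medication are followed until the events resolve or need no further action. Study doctors are also directed to discontinue patients with intolerable events, so the decision is not the patient's alone. This stands too, and it limits the point to the Y-BOCS and HDRS-17 change scores.

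**The numbers.** The five may not all be discontinued for doing badly. The plan has 10 per group, so some could be lost before randomisation and others lost to follow-up. Not all would return even if paid. The six-point criterion measures worsening from a patient's own baseline, so it does not calibrate a difference from completers. The range in the working is therefore an illustration, not an estimate.

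**Cognitive testing.** If the condition refers to the Week 0 session, a patient at Week 4 will normally have met it already. That is possible. The text does not say so, and this is a reason to clarify it.

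**Other documents.** The consent form may give fuller payment terms. I have not seen it. It would not by itself add efficacy ratings to the return visit or tell the SAP to use them.

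**Conclusion.** The concern holds as a gap in outcome collection, with an unclear payment rule attached. The return visit after discontinuation names safety assessments alone, while the SAP needs a Week 4 Y-BOCS and HDRS-17 from each patient. Followed as written, those scores may be missing mainly in patients removed for poor tolerability or worsening OCD, and the mean change could look too favourable.

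The size is unknown. The 0.6 to 1.8 points assume that all five projected non-completers were treated, lack Week 4 scores, and improved by 3 to 9 points less than the rest. With fewer such patients or a smaller difference the bias shrinks in proportion. It vanishes if the return visit is already meant to include the ratings. It is not established that the payment rule would cause dropout, or that paying would recover every missing score.

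The amendment is worth making because it is cheap and uses a visit already requested, and because the SAP has no means of repairing the loss afterwards.

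**What to change.** - **Protocol, Criteria for Early Discontinuation.** State that the return visit takes place at the scheduled Week 4 time and includes the independent evaluator's Y-BOCS and HDRS-17 alongside the safety assessments. The discontinuation criteria themselves need no change.
- **SAP, Statistical Analysis Plan.** State that these scores enter the Week 0 to Week 4 change scores whether or not nabilone was stopped, and report by arm how many patients discontinued and how many lack a Week 4 score.
- **Protocol, Compensation and/or Reimbursement.** State that the Week 4 evaluation is offered and paid whether or not nabilone was stopped. Do not make that payment depend on cognitive testing. If the testing is kept, describe it in Study Procedures and Assessment Instruments.

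Keep the payment at Week 4. Splitting the $100 equally over Weeks 1 to 4 might seem fairer, but it would leave $100 / 4 = $25 for the one rating the analysis depends on.

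The cost is a short amendment, up to about $500 if all five projected non-completers are paid, and about 50 minutes of rating per returning patient. No new visit or staff is needed. One limitation remains: scores taken after stopping describe the patient's course after assignment rather than on nabilone, and the report should say so.

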Cannabinoid Medication for Adults with OCD

NCT02911324

5/23/2016

Study Summary: The purpose of this pilot research study is to test whether a medication called nabilone (Cesamet) on its own or in combination with a form of cognitive-behavioral therapy (CBT) called exposure and response prevention (EX/RP) does not cause unpleasant side effects in participants with obsessive-compulsive disorder (OCD), and to see if participants with OCD find it easy to take the medication repeatedly to help them feel better. Nabilone is a synthetic cannabinoid; it acts on the brain's "endocannabinoid system," which has been hypothesized to play a role in OCD. Nabilone is approved by the FDA for the treatment of chemotherapy-induced nausea and vomiting. It is not FDA-approved for treating OCD.

Study Design

Conditions or Focus of Study: Obsessive-Compulsive Disorder

Study Type: Interventional

Primary Purpose: Treatment

Study Phase: Phase 1/2 (for trials that are a combination of phases 1 and 2)

Intervention Model: Parallel (participants assigned to one of two or more groups in parallel for the duration of the study)

Number of Arms: 2 (number of intervention groups)

Masking: Open Label (no masking is used; all involved know the identity of the intervention assignment)

Allocation: Randomized

Enrollment: Number of Subjects: 25 Type: Anticipated

Arm Label: Nabilone

Arm Type: Experimental

Arm Description: Will receive nabilone at 1 mg BID over 4 weeks

Arm Label: Nabilone and EX/RP

Arm Type: Experimental

Arm Description: Will receive nabilone at 1 mg BID plus therapist-guided Exposure and Response Prevention Therapy over 4 weeks.

Inclusion/Exclusion

Gender: Both

Age Limits: 18-60

Accepts Healthy Volunteers?: No

Inclusion Criteria:

- Age 18-60
- Physically healthy, not pregnant
- Primary OCD
- Patient off all psychotropic medication (except selective serotonin reuptake inhibitors) and any other medication likely to interact with nabilone
- Ability to provide informed consent
- Ability to tolerate a treatment free-period

Exclusion Criteria:

- History of violence
- Lifetime history of psychosis or bipolar disorder
- Lifetime history of intellectual disability
- Severe depression or suicide risk
- Females who are pregnant or nursing
- Patients planning to begin EX/RP or currently in EX/RP
- Current substance use disorder or positive urine toxicology at screening, or any adverse reaction to a cannabinoid
- History of any significant medical condition that may increase the risk of participation

Interventions

Intervention Name (use generic name if established): Nabilone

Intervention Type: Drug

Intervention Description (do not repeat information already included in arm/group descriptions): Nabilone is a synthetic form of THC and cannabinoid 1 receptor agonist. It acts on the brain's "endocannabinoid system," which has been hypothesized to play a role in OCD.

Intervention Name: Exposure and Response Prevention Therapy

Intervention Type: Behavioral

Intervention Description: Exposure and Response Prevention Therapy (EX/RP) is a type of Cognitive-Behavioral Therapy for OCD that involves intentionally confronting situations that trigger obsessional distress while refraining from doing compulsions.

Outcome Measures

Primary Outcome Measure 1: Feasibility of recruitment of patients with OCD into a study of nabilone

Time Frame: Total participants who consent to participate for the duration of the study

Safety Issue (Is this outcome measure assessing a safety issue?): No

Primary Outcome Measure 2: Tolerability of nabilone (e.g. adverse events reported)

Time Frame: Baseline (Week 0), Week 1, Week 2, Week 3, Week 4

Safety Issue (Is this outcome measure assessing a safety issue?): Yes

Primary Outcome Measure 3: Yale-Brown Obsessive-Compulsive Scale (YBOCS)

Time Frame: Weeks 0 and 4

Safety Issue (Is this outcome measure assessing a safety issue?): No

Secondary Outcome Measures: Hamilton Depression Rating Scale, 17-Item (HDRS-17)

Time Frame: Weeks 0 and 4

Safety Issue?: No

Statistical Analysis Plan

For both the YBOCS and HDRS-17 measures, we will calculate change scores for the nabilone and nabilone+EX/RP groups based on the difference between Baseline (Week 0) and Week 4. This preliminary study is not designed to assess for statistical differences between groups, and thus only the overall magnitude of change between groups will be compared. We will assess feasibility of recruitment based on the total number of participants enrolled over the duration of the study. Finally, we will assess nabilone's tolerability in OCD based on weekly self-reporting of side effects using a checklist drawn from the nabilone package insert, and any other adverse events that occur over the course of the study.

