## Assessment Instruments

Create a table or give a brief description of the instruments that will be used for assessment

- Structured Clinical Interview for DSM-5 (SCID, 1-2 hours) The SCID is a semi-structured clinician rated instrument that assesses the major adult Axis I disorders in DSM-5
- Yale-Brown Obsessive Compulsive Scale (Y-BOCS, 45 minutes) This is a semi-structured clinician rated instrument used to measure obsessions and compulsions separately over five separate dimensions (time consumed, distress, interference, degree of resistance, control). This is the gold-standard measure of OCD

symptoms.

- Clinical Global Impression (CGI, 1 minute). This is a clinician rated instrument for rating global psychopathological severity.
- 17-Item Hamilton Depression Rating Scale (HDRS-17, 5 minutes). This is a clinician rated instrument for rating depression.
- Sao Paulo Sensory Phenomena Scale (SPSPS, 6 minutes). This is a clinician rated instrument for rating sensory phenomena associated with OCD.
- Depression Anxiety Stress Scales (DASS, 5 minutes): 21-item self-report measure that assesses depression, anxiety, and stress experienced in the past week.
- Quality of Life Enjoyment and Satisfaction Measure (Q-LES-Q, 4 minutes): Self-report questionnaire that assesses subjects' satisfaction and enjoyment in daily life.
- PhenX Toolkit Hand Dominance Measure: This measure assesses one's handedness, and is based off of the Edinburgh Handedness Inventory (2 minutes)
- Intolerance of Uncertainty Scale: 27-item self-report questionnaire that assesses a person's ability to tolerate uncertainty. (4 minutes)
- Spielberger State-Trait Anxiety Inventory (STAI): 40 item self-report questions that assesses state and trait anxiety (6 minutes)
- Patient EX/RP Adherence Scale (PEAS, 5 minutes): This 3-item scale is used by a therapist to assess subject adherence to EX/RP homework and targets the quantity and quality of exposures and the degree of ritual prevention.
- Side Effect Checklist (SECL, 3 minutes): Side Effect Assessment: possible side effects will be rated on a scale from 0 (none) to 3 (severe). Weight, blood pressure and heart rate will be assessed at each visit.

Please attach copies, unless standard instruments are used

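### The plan does not mask the independent evaluator who rates Y-BOCS and HDRS-17, leaving the Week 0 to Week 4 comparison between arms open to an avoidable rater-expectation bias

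*SAP*

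**What the plan says.** The SAP (Study Design, Masking) classes the trial as "Open Label (no masking is used; all involved know the identity of the intervention assignment".

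The protocol (Study Procedures, Assessments) assigns the ratings to an independent evaluator "who is not involved with study treatment will assess global psychopathology (CGI"), and the same list includes the Y-BOCS and the Hamilton depression scale. The section on minimizing risks mentions this evaluator again, as a weekly monitor alongside the study physicians. Neither place says that the evaluator is kept unaware of arm. The available text has no instruction to participants or staff not to disclose the arm, and no record of unmasking.

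Both scales depend on the rater. Of the Y-BOCS the protocol (Assessment Instruments) says "This is a semi-structured clinician rated instrument used to measure obsessions and compulsions separately"; of the HDRS-17, "This is a clinician rated instrument for rating depression".

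On timing, the protocol states "After the baseline evaluation, participants will be randomized to one of two groups". The arms differ in psychotherapy only: "Group 2 (n=10) will receive nabilone at 1 mg BID plus therapist-guided EX/RP", while Group 1 takes nabilone at the same stated dose without EX/RP.

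The SAP lists "Primary Outcome Measure 3: Yale-Brown Obsessive-Compulsive Scale (YBOCS") and makes the HDRS-17 the secondary outcome, both at Weeks 0 and 4. It plans change scores by arm, no hypothesis test, and says that "only the overall magnitude of change between groups will be compared".

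**The concern.** Separating the rater from treatment is not the same as masking the rater. Someone who delivers no therapy can still know who is receiving it, and on the SAP's wording does know. The protocol describes EX/RP as an established treatment of first choice and nabilone as a new approach under test, so a rater could well expect different results in the two arms. On a semi-structured, clinician-rated scale that expectation can move the score.

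At stake is the one between-arm comparison that the SAP plans. It covers two outcomes, and this evaluator rates both. Calling it descriptive removes any question of type I error but not of bias, since a descriptive difference is taken at face value. The protocol's background section says that the pilot data are meant to back later grant applications, so a distorted difference could carry into the planning of the next trial.

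**Working it through.** The plan gives no effect size, standard deviation, alpha or power for these outcomes, so there is no stated figure to reproduce. The check is whether the design would remove a rater shift by itself, and how much of the analysis is exposed.

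**Inputs**

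- Masking: none (SAP, Study Design).
- Rater of both scales: the independent evaluator, masking not stated (Protocol, Study Procedures).
- Order of events: baseline evaluation, then randomization (Protocol, Study Procedures). The SAP equates baseline with Week 0.
- Analysis: Week 0 to Week 4 change, compared between arms (SAP, Statistical Analysis Plan).
- Size: 10 per arm, 20 completers (Protocol, Background and Description of Subject Population).

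**Does the change score cancel the shift?**

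The reported contrast is

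D = (Week 4 − Week 0 in Group 2) − (Week 4 − Week 0 in Group 1).

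Let s1 and s2 be the average amounts by which knowledge of the arm moves the Week 4 rating in Groups 1 and 2. No arm exists when Week 0 is rated, so the corresponding shift there is 0 in both groups. Then

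bias in D = (s2 − 0) − (s1 − 0) = s2 − s1.

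- If s1 = s2, the bias is 0: a shift common to both arms cancels.
- If s1 ≠ s2, the whole difference appears in D.
- The sample size does not enter the expression, so more participants would not reduce it.

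For contrast, the sampling error of D does depend on n. At 10 per arm it is SD × √(1/10 + 1/10) = 0.447 SD, where SD is the standard deviation of the change score. The documents do not give that SD, so the result stays in SD units.

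**How much is exposed?**

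- Outcomes compared between arms: Y-BOCS and HDRS-17, both rated by this evaluator = 2 of 2.
- Primary outcomes: recruitment feasibility, tolerability, Y-BOCS. Only the Y-BOCS is affected = 1 of 3.
- Planned Week 4 ratings: 2 scales × (10 + 10) = 40.

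**Can this role be masked?**

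Both arms take nabilone at the same stated dose, so drug effects do not by themselves tell the arms apart. What distinguishes them is mainly attendance at the 9 EX/RP sessions, which an evaluator outside the treatment team need not see or be told about.

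**The case against.** The strongest reply is that the SAP entry is registry language. Its neighbouring fields carry the same kind of generic gloss, and the statement that everyone knows the assignment may simply define the open-label category. The SAP is dated 5/23/2016 and the protocol 1/7/2020; the later document separates the rater from treatment, which is a partial safeguard. On this reading the documents show only that masking of the rater is undocumented. That stands as a limit on the claim: this is a documented risk, not proven bias. It does not dispose of the point, because the SAP line is the only statement on masking in the available text and the protocol does not correct it. If the evaluator was masked, the record understates the trial's quality and still needs changing.

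Second, the comparison matters less than usual. The aims are feasibility and tolerability, no test or decision rule uses the Y-BOCS, and 10 per arm gives an imprecise contrast in any case. With nabilone in both arms and neither a placebo nor an EX/RP-alone arm, the contrast reflects the addition of EX/RP and cannot isolate nabilone; masking to arm would not remove a rater's expectations about nabilone itself. All of this is fair and limits the severity. Yet the Y-BOCS is a listed primary outcome, and imprecision does not excuse a bias that is cheap to prevent.

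Third, masking would be imperfect. Group 2 participants may mention therapy when asked about resistance and control, and their own expectations will still colour their answers. That also stands: masking the rater closes one of two routes by which expectation enters, not both.

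**Conclusion.** The concern holds. As written, the plan leaves the rater of both compared outcomes aware of arm at Week 4 but not at Week 0, and the change score passes any arm-specific rater shift in full into the between-arm difference. Exposure is 2 of 2 compared outcomes, 1 of 3 primary outcomes and 40 planned Week 4 ratings. The size and direction of any bias are unknown.

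This rests on three assumptions: the SAP masking entry is taken at its word; the Week 0 ratings are those of the baseline evaluation that precedes randomization; and the pages removed from the public documents say nothing about masking the evaluator. The change should be made, but the matter is not critical: the comparison is descriptive, recruitment is unaffected, and tolerability rests mainly on self-report. Confidence is medium, because the evaluator may have been masked in practice without this being recorded.

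**What to change.** First establish what is, or was, done about the evaluator's knowledge of arm; then make the documents say so.

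- **If the evaluator is masked, or masking can still be introduced:** change the SAP masking entry to outcomes assessor masked, participants and treating staff open. In the protocol's Assessments paragraph, state that the evaluator is not told the arm, that participants and staff are instructed not to disclose it or mention therapy sessions during ratings, and that any unmasking is logged by arm and visit.
- **If ratings were made unmasked:** leave the SAP entry as it is, say plainly that the evaluator knew the arm, and report this as a limitation of the Y-BOCS and HDRS-17 comparison. Changing the entry in that case would create a false record.

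The cost is one SAP line, a sentence or two in the protocol and a simple log. The protocol already names an evaluator outside the treatment team, so no new role is needed on paper; whether current staffing suffices is not documented. Treatment, visit schedule and sample size stay as they are. The downside is that some accidental unmasking will occur and has to be recorded and reported.
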